3.2 Estimated Duration of Subject Participation

Subjects will be in this study for approximately 168 weeks (156 weeks for treatment and 12 weeks for follow-up).

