- 2. Study Abstract (Study Design, Treatment Regimen), Section 1.3 (Research Hypothesis), Section 3.1 (Overview of Study Design), Figure 3.1-1 (Study Flow Diagram), Section 3.4.1 (Rationale for Study Design), Section 3.4.2 (Rationale for MEDI-546 Dose), Section 4.5.3 (Treatment Regimen), Section 4.5.4.1 (Dose Calculation), Table 4.5.4.1-1 (Dose Calculation for MEDI-546 Drug Product for IV Infusion), and Section 5.1 (Schedule of Study Procedures) changed dose of MEDI-546 from 1000 to 300 mg as the efficacy and safety data from Study CD-IA-MEDI-546-1013 indicated that the 300 mg dose had a more favorable benefit:risk profile than the 1000 mg dose for subjects with chronic, moderately-to-severely active SLE.
- 3. Study Abstract (Study Design), Section 3.1 (Overview of Study Design), Figure 3.1-1 (Study Flow Diagram), and Section 4.5.5 (Treatment Administration) changed IV

infusion time from approximately 60 minutes to at least 30 minutes as the efficacy and safety data from Study CD-IA-MEDI-546-1013 indicated that the 300 mg dose had a more favorable benefit:risk profile than the 1000 mg dose for subjects with chronic, moderately-to-severely active SLE.

- Study Abstract (Study Design, Treatment Regimen), Section 3.1 (Overview of Study Design), Figure 3.1-1 (Study Flow Diagram), and Section 4.5.3 (Treatment Regimen) changed the duration of investigational product administration from 2 to 3 years. This change was made to collect more long-term safety data with MEDI-546.
- 5. Study Abstract (Study Design), Section 3.1 (Overview of Study Design) and Section 3.4.2 (Rationale for MEDI-546 Dose) removed sentence that stated that as additional MEDI-546 data became available, if another dose is determined to be the optimal dose, the protocol would be amended. This change was made based on efficacy and safety data from Study CD-IA-MEDI-546-1013 that indicated that the 300 mg dose had a more favorable benefit:risk profile than the 1000 mg dose for subjects with chronic, moderately-to-severely active SLE.
- Study Abstract (Sample Size and Power Calculations), Section 1.2.3 (Summary of Clinical Experience), and Section 7.5 (Sample Size and Power Calculation) - updated sections to state that a total of 307 subjects have been randomized in Study CD-IA-MEDI-546-1013.

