2 STUDY OVERVIEW

2.1 Study Objectives

2.1.1 Primary Study Objective(s)

The primary objective of this study is to evaluate the long-term safety and tolerability of intravenous (IV) anifrolumab in adult subjects with moderately-to-severely active SLE.

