2.4 Sample Size

Sample size estimation is based on the number of subjects who have completed the treatment period of study CD1013. A total of 307 subjects have been randomized in study CD1013. Assuming that 20% of subjects will be lost to follow up or discontinue from study CD1013, there will be a total of approximately 240 subjects who will be eligible for this long-term safety study.

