3.3 Study Subjects

3.3.1 Subject Disposition and Completion Status

The number of subjects enrolled in the CD1145 study will be summarized overall and by site number. In addition, disposition of subjects throughout the CD1145 study with respect to completion of treatment will be provided overall and overtime (year 1, year 2, year 3). Disposition of subjects with respect to completion of study will also be provided.

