3.8.4 Exposure Adjusted Adverse Events Rate

The exposure adjusted rate (per 100 patient-year) for treatment emergent AEs, non-serious AEs, acute AEs, investigational product related AEs, AEs by highest severity, AEs leading to treatment discontinuation, AEs resulting in death, SAEs and AESIs will be summarized. The exposure adjusted subject rate per 100 patient-years is defined as [the number of subjects with an event/(total exposure time in days/365.25)]*100.

For treatment emergent AEs leading to treatment discontinuation, AEs resulting in death, SAEs and AESIs, duration of exposure is calculated as follows:

- Anifrolumab Total group: duration of exposure (days) = minimum(end of study date in CD1145, last dosing date in CD1145+85 days) – first dosing date in CD1145+1.

- Anifrolumab 1000 mg group:
 - For subjects who received 1000 mg only during the study: duration of exposure (days) = minimum(end of study date in CD1145, last dosing date in CD1145+85 days) – first dosing date in CD1145+1.
 - For subjects who received both 1000 mg and 300 mg during the study: duration of exposure (days) = (first dosing date of 300 mg – 1) – first dosing date in CD1145 + 1.
- Anifrolumab 300 mg group: duration of exposure (days) = minimum(end of study date in CD1145, last dosing date in CD1145+85 days) – first dosing date of 300 mg +1.

The AEs leading to treatment discontinuation, AEs resulting in death, SAEs and AESIs occurred during the exposure period will be included in the summary.

The non-serious AEs are captured during the first year of subject's participation only. So for treatment emergent AEs, non-serious AEs, acute AEs, investigational product related AEs, and AEs by highest severity, duration of exposure is calculated as follows:

- Anifrolumab Total group: duration of exposure (days) = minimum(end of study date in CD1145, first dosing date in CD1145+364) – first dosing date in CD1145+1.
- Anifrolumab 1000 mg group:
 - For subjects who received 1000 mg only during the study: duration of exposure (days) = minimum(end of study date in CD1145, first dosing date in CD1145+364) – first dosing date in CD1145+1.
 - For subjects who received both 1000 mg and 300 mg during the study: duration of exposure (days) = minimum(first dosing date in CD1145+364, first dosing date of 300 mg-1) – first dosing date in CD1145 + 1.
- Anifrolumab 300 mg group: minimum(end of study date in CD1145, first dosing date in CD1145+364) - first dosing date of 300 mg +1.

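### SAP 3.8.4 gives SAE and AESI rates over one period of up to about 3.2 years and none by time since first dose, so a change in risk with longer treatment is diluted overall and mixed with the dose switch by dose group

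*SAP*

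**What the plan says.** The SAP's primary objective (2.1.1) is "to evaluate the long-term safety and tolerability of intravenous (IV) anifrolumab". Protocol Amendment 4 lengthened treatment from 2 to 3 years, and the Protocol's amendment summary gives the reason: "This change was made to collect more long-term safety data with MEDI-546". Protocol 3.2 states the planned stay: "Subjects will be in this study for approximately 168 weeks (156 weeks for treatment and 12 weeks for follow-up".

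Protocol 6.1.1 has SAEs and AESIs collected for the whole of participation. Non-serious AEs are routinely collected only in the first year.

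SAP 3.8.4 defines the rate as subjects with an event divided by total exposure time, per 100 patient-years. For AEs leading to discontinuation, deaths, SAEs and AESIs, the Total group's exposure runs from first dose to the earlier of end of study and last dose plus 85 days. The events that count are set by the same window: "The AEs leading to treatment discontinuation, AEs resulting in death, SAEs and AESIs occurred during the exposure period will be included in the summary". SAP 3.2.2 shows these rates for 300 mg, 1000 mg and Total. In subjects who received both doses, 1000 mg time stops the day before the first 300 mg dose.

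SAP 3.8.1 to 3.8.3 add AE, AESI, death and discontinuation summaries with no period stated. The AE subgroups in 3.8.7 are interferon signature and ADA status. No time-to-event analysis of AEs is specified. Laboratory values, vital signs, ECG and Cushingoid features are summarised by visit, and SAP 3.3.1 splits disposition by year: "with respect to completion of treatment will be provided overall and overtime (year 1, year 2, year 3".

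**The concern.** The question that only an extension can answer is whether serious or special-interest risk changes as treatment continues. A rate pooled over the whole period is a valid average for that period but carries no information on timing. A late rise, an early cluster that fades and a steady risk can all produce the same figure.

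The by-dose rates do not fill the gap. In subjects who switched, 1000 mg time is early and 300 mg time is late. A rise with duration would appear as a worse 300 mg rate, and an early cluster as a worse 1000 mg rate.

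At stake is how much the later exposure, which Amendment 4 was written to obtain, contributes to the reported safety conclusion. Disposition will show how many subjects remained in each year, but no planned output will show their serious-event rate in that year.

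**Working it through.** **1. The plan's own figure.** SAP 2.4 starts from the parent study: "A total of 307 subjects have been randomized in study CD1013". It then allows for a 20% loss in the parent study and arrives at about 240 for the extension. 307 × (1 − 0.20) = 245.6, against about 240 stated (difference 5.6, or 2.3%). It reproduces, and 240 is used below. The documents give no SAE or AESI rate and no drop-out rate for the extension.

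**2. Longest exposure window.** The last scheduled dose is at Week 156. With the 85-day tail and the SAP's +1: 156 × 7 + 85 + 1 = 1178 days; 1178 / 365.25 = 3.23 years. The 168 weeks in Protocol 3.2 are 1176 days, which agrees.

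**3. Person-years by period.** Assume that exposure ends at a constant yearly proportion d. With h = −ln(1 − d), person-years between times a and b are 240 × (exp(−ha) − exp(−hb)) / h, or 240 × (b − a) when d = 0. The periods are 0–1, 1–2 and 2–3.23 years.

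**4. Pooled rate.** This is the person-year-weighted mean of the period rates. Two illustrative patterns per 100 patient-years are compared: a late rise (1, 1, 3) and an early cluster that fades (3, 1, 1).

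| Yearly drop-out (assumed) | Person-years by period | Total | Share after year 2 | 1, 1, 3 pools to | 3, 1, 1 pools to |
|---|---|---|---|---|---|
| 0% | 240.0 / 240.0 / 294.0 | 774.0 | 38% | 1.76 | 1.62 |
| 10% | 227.8 / 205.0 / 223.4 | 656.2 | 34% | 1.68 | 1.69 |
| 20% | 215.1 / 172.1 / 164.7 | 551.9 | 30% | 1.60 | 1.78 |
| 25% | 208.6 / 156.4 / 139.4 | 504.4 | 28% | 1.55 | 1.83 |

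At 10%: (227.8 + 205.0 + 3 × 223.4) / 656.2 = 1103.0 / 656.2 = 1.68, and (3 × 227.8 + 205.0 + 223.4) / 656.2 = 1111.8 / 656.2 = 1.69. A steady rate of about 1.7 would give the same figure.

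**5. Dilution of the late rate.** Against a true late rate of 3, the pooled rate is low by 1 − 1.76/3 = 41% (no drop-out) to 1 − 1.55/3 = 48% (25% a year). It still stands 1.55 to 1.76 times above the early rate of 1.

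**6. Effect of counting subjects.** Each subject counts once and exposure is not stopped at the first event. With a constant rate λ per year and full retention, the SAP formula gives 100 × (1 − exp(−3.23λ)) / 3.23. For λ = 0.005 this is 0.496 against a true 0.5, which is negligible. For λ = 0.10 it is 8.5 against 10, and 1 − exp(−0.2) = 18% of subjects enter year 3 already counted, so their later events add nothing. Steps 4 and 5 are therefore close for rare events and slightly understate the problem for common ones.

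**7. What a by-year split could show.** With 20% yearly drop-out, a base of 0.5 per 100 patient-years and a threefold late rise, expected events are 0.005 × 215.1 = 1.1, 0.005 × 172.1 = 0.9 and 0.015 × 164.7 = 2.5. A one-sided 0.025 conditional test of late against earlier time, by simulation, has power of about 8%. That becomes 26% at a base of 1 and 93% at a base of 5. Three subjects with an event in 139.4 person-years (the 25% case) give 100 × 3 / 139.4 = 2.2 per 100 patient-years. The exact 95% Poisson limits on a count of 3 are 0.619 and 8.767, that is 0.4 to 6.3 per 100 patient-years.

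**The case against.** The best defence is that the plan is less blunt than it looks. Four stronger readings are tempting, and the documents do not support them.

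- **That the plan reports a single rate.** It reports three, and in switched subjects the two dose columns partly separate early from late time. That is correct, but dose and time cannot be told apart there, so the columns do not replace a split by time.
- **That the pooled rate leans to early exposure.** This depends on drop-out, which the documents do not state; the 20% in SAP 2.4 concerns the parent study. With full retention, time after year 2 carries the most weight, at 38%.
- **That a late rise, in malignancy for example, could not be seen.** It is diluted, not erased. SAP 3.1 plans data listings, SAP 3.8.3 lists deaths and discontinuation AEs, and Protocol Appendix 5 has the DSMB review AEs and AESIs, including malignancy, periodically in tables and listings. Individual late cases stay visible. None of these is specified as a rate with a person-time denominator by time on drug.
- **That the long-term conclusion should rest on by-year rates.** Events will be sparse, later years contain only those who stayed, the dose changed during the study and there is no control arm. By-year rates are a supplement.

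It can also be said that Protocol 7.3.1 rules out formal testing, so low power is no defect. That stands, and it argues for intervals and cautious wording rather than for leaving the display out. Finally, SAP section 1 defers table templates to a separate programming plan, which could contain such a table. The SAP itself does not call for one.

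**Conclusion.** The point holds as a gap in what is prespecified. The SAP calls for no SAE, AESI, death or discontinuation-AE summary by time since first dose, in a study whose primary objective is long-term safety and whose disposition is already split by year. The Total rate dilutes a change in risk, and the by-dose rates confound it with the switch from 1000 mg to 300 mg.

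In the illustration, a late tripling is understated by 41% to 48% and is hard to tell from its mirror image. The sizes rest on assumed values: 0% to 25% yearly drop-out at a constant rate, 240 subjects, the full 3.23-year window and the chosen rate patterns. The lack of timing information in the pooled figure does not depend on them.

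The pooled rate is not wrong and should stay. This is an inexpensive improvement to the reporting, not a flaw that invalidates the analysis.

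**What to change.** In SAP 3.8.4, for SAEs, deaths, each AESI type and AEs leading to treatment discontinuation, add one descriptive table by year since first extension dose: Days 1–365, Days 366–730, and after Day 730 to the end of exposure. For each interval show:

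- subjects at risk at its start;
- subjects with an event in it;
- person-years within it;
- the rate per 100 patient-years with an exact confidence interval.

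State that a subject may count once in each interval, so interval counts need not add up to the pooled count. Show study day of onset in the AE listings.

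Keep the pooled rate and read the by-year rates beside it, with caveats for the dose change, selective retention and the absence of a control arm. Leave non-serious AEs out, because they are not routinely captured after year 1.

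The cost is a paragraph of SAP text and one table from dates already used in 3.8.4, with no new data collection. The downside is wide intervals for rare AESIs in the last period, which the text should acknowledge.

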3.4.2 Rationale for MEDI-546 Dose

4 SUBJECT SELECTION, TREATMENT, AND WITHDRAWAL

4.1 Subject Participation and Identification

Study participation begins once written informed consent is obtained (see Section 10.3 for details) for this OLE study. Once informed consent is obtained, a subject identification (SID) number will be assigned to each subject by a central system interactive voice/web response system (IVRS/IWRS). The SID number will be used to identify the subject during the screening process and throughout study participation, if applicable.

A master log of all consented subjects will be maintained at the site and will document all pretreatment period failures (ie, subjects who are consented but do not meet study eligibility criteria), including the reason(s) for pretreatment period failure (see Section 9.1 for details).

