Subjects who are permanently discontinued from receiving investigational product will be followed for safety per Section 6.4, including the collection of any protocol-specified blood or urine specimens, unless consent is withdrawn or the subject is lost to follow-up or enrolled in another clinical study. Twenty-eight days (\pm 7 days) after the last dose of investigational product, subjects will begin the follow-up period by completing the Visit 41/Early Discontinuation Visit assessments. Two subsequent follow-up visits will also be completed 59 and 85 days (\pm 7 days) after the last dose of investigational product as per the schedule of study procedures. A subject who receives any SLE medication or SLE treatment listed in Appendix 3 (other than those prohibited medications or treatments listed above) may be allowed to continue receiving investigational product only if permission from the sponsor is obtained.

Concomitant medications that require the sponsor to be notified immediately and the medical monitor to be consulted to determine if a subject may continue to receive investigational product include, but are not limited to:

- Corticosteroids with a long biologic half-life (eg, dexamethasone, betamethasone)
- Increase in oral corticosteroids (OCS) treatment above a total dose > 40 mg/day for a dosing period > 14 days, dosing with MEDI-546 may be continued, unless there is a safety concern. However, it should be noted that frequent steroid use above Study CD-IA-MEDI-546-1013 baseline for SLE disease control (> 2 times every 6 months, higher doses [> 40 mg/day], and/or longer duration than permitted by the protocol) after 12 months of open-label MEDI-546 should result in discontinuation of MEDI-546 administration for failure to achieve a favorable benefit:risk profile.

Withdrawal of consent: If consent is withdrawn, the subject will not receive any further investigational product or further study observation. Note that the subject may need to undergo additional tests or tapering of treatment to withdraw safely.

Lost to follow-up: Subjects will be considered lost to follow-up only if no contact has been established by the time the study is completed (as defined in Section 4.9) such that there is insufficient information to determine the subjects' status as of their last visit.

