The events occurred during the exposure period will be included in the summary.

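### SAP 3.8.4 ends the first-year exposure window a year after first dose, but routine non-serious AE capture ends a year after consent, so the Total-group non-serious AE rate is slightly understated whenever consent precedes dosing

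*SAP*

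**What the plan says.** SAP 3.8.4 defines the exposure-adjusted rate as subjects with an event over person-time: "the number of subjects with an event/(total exposure time in days/365.25)]*100". It then gives two sets of exposure formulas.

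- **Whole-study set** (AEs leading to discontinuation, deaths, SAEs, AESIs). For the Total group: "minimum(end of study date in CD1145, last dosing date in CD1145+85 days) – first dosing date in CD1145+1".
- **First-year set** (treatment-emergent, non-serious, acute, related, and by severity). For the Total group, exposure ends at "minimum(end of study date in CD1145, first dosing date in CD1145+364", with days counted from first dose, both ends included. The SAP's reason for this shorter window is that non-serious AEs are captured only in the first year of participation. On the numerator it says: "The events occurred during the exposure period will be included in the summary".

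The protocol fixes the start of that year in Section 4.1: "Study participation begins once written informed consent is obtained". Sections 6.1.1 and 6.4.1 limit non-serious AE capture to the first year of participation. The exceptions are events that lead to interruption of investigational product or to discontinuation; like SAEs and AESIs, these are recorded throughout. Section 6.4.1 runs AE reporting from consent to the end of the subject's participation.

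On lost subjects, Protocol 4.2.3 says: "Subjects will be considered lost to follow-up only if no contact has been established by the time the study is completed". The SAP does not define the end-of-study date for them.

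**The concern.** The first-year window exists to match person-time to the period in which non-serious AEs were recorded. The two periods end on different days. The denominator stops 364 days after first dose, and routine capture stops 364 days after consent. Starting the clock at first dose is correct for treatment-emergent events, so the misfit lies only at the end of the window.

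Any gap between consent and first dose becomes a tail with person-time but no routine non-serious capture. That lowers the rate, which is the unfavourable direction in a study whose primary objective is long-term safety and whose results are purely descriptive.

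The by-dose rates are more exposed. For a subject who switches from 1000 mg to 300 mg within year 1, 1000 mg time stops the day before the first 300 mg dose. The whole uncovered tail then falls in the shorter 300 mg denominator.

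**Working it through.** The documents give no AE rate or person-time total to reproduce. The SAP's own full-year maximum is (first dose + 364) − first dose + 1 = 365 days.

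**1. Can consent precede first dose?** Yes.
- Protocol 5.1.1 describes a pretreatment period.
- Protocol 5.1.2.1 separates consent from the procedures that must fall on the dosing day.
- Protocol 6.1.1 defines nontreatment-emergent AEs as those between consent and first dose.

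The gap itself is not stated. Protocol 3.1 expects first dose within 28 days of Day 422 of the parent study. Protocol 5.2.1 collects history from Day 422 up to consent, which places consent at or after Day 422. For starts inside that window, an assumed gap g of 0 to 28 days is therefore reasonable.

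**2. Uncovered tail, Total group, full-year subject.** Uncovered days = (first dose + 364) − (consent + 364) = g. The routine events recorded do not change, so the SAP rate divided by the matched rate is (365 − g)/365.

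| g (days, assumed) | Days with capture | Uncovered share, g/365 | SAP rate / matched rate |
|---|---|---|---|
| 0 | 365 | 0% | 1.000 |
| 7 | 358 | 1.9% | 0.981 |
| 14 | 351 | 3.8% | 0.962 |
| 28 | 337 | 7.7% | 0.923 |

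Early stoppers dilute this, because their window closes before the tail. Assume 5% to 30% stop in year 1, with last dose 140 days after first dose and the final visit 7 days late (140 + 85 + 7 + 1 = 233 days each). With g = 28 for everyone else:
- 5% stopping: (0.95 × 337 + 0.05 × 233)/(0.95 × 365 + 0.05 × 233) = 0.926
- 30% stopping: (0.70 × 337 + 0.30 × 233)/(0.70 × 365 + 0.30 × 233) = 0.940

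**3. 300 mg group.** Assume 300 mg starts on Day 253, which is 252 days after first dose. The first-year 300 mg window is 364 − 252 + 1 = 113 days. A 14-day tail is 14/113 = 12% of it, and a 28-day tail is 28/113 = 25%.

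**4. Missing last-dose+85 limit, subject followed on schedule.** The final visit is due 85 ± 7 days after last dose. With that visit 7 days late:

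| Last dose (days after first) | SAP days | With +85 limit |
|---|---|---|
| 0 | 93 | 86 |
| 84 | 177 | 170 |
| 252 | 345 | 338 |
| 279 or later | 365 | 365 |

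The difference is at most 7 days. With 5% to 30% stopping as in step 2, the limit removes 0.1% to 0.7% of total person-time.

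**5. Missing limit, lost subject.** The effect depends on the undefined end-of-study date. If that date were study completion, a subject last dosed on Day 57 (56 days after first dose) would count 365 days instead of 56 + 85 + 1 = 142. If it is last contact, this excess disappears.

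**The case against.** **Consent may fall on Day 1.** The schedule lists consent under Visit 1, and its first-year sampling weeks are counted from Day 1. If consent and dosing share a day, nothing is wrong. This stands: the gap is an assumption, and the 28 days in Protocol 3.1 run from Day 422, not from consent. A reader might infer longer gaps from late starts approved by the medical monitor, but nothing says that those subjects consented early.

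**The limit's absence does not itself count unrecordable time.** A reader might infer that every day beyond last dose+85 is empty. Protocol 6.4.1 collects AEs to the end of participation, and the SAP counts events in the exposure period, so within year 1 those days have both capture and person-time. This also stands. The omission is an inconsistency between two definitions. It matters only for lost subjects, and only if their end-of-study date is set after last contact. Protocol 4.2.3 says when loss may be declared, not which date is recorded, and it classes subjects who refuse to return as withdrawals, which shrinks the lost group.

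**Not every first-year rate falls by the uncovered share.** SAEs, AESIs and AEs causing interruption or discontinuation are captured throughout, so the treatment-emergent, related and severity rates are only partly affected. The numerator counts subjects, so a missed late event matters only for a subject without an earlier one. As an illustration, assume a constant hazard and one-year incidence p. The share of affected subjects missed with g = 28 is [(1 − p)^(337/365) − (1 − p)]/p, which is about 4% at p = 0.7 and 2% at p = 0.9. The shortfall against complete 365-day capture is thus smaller than the 7.7% shortfall against a matched window.

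**Conclusion.** The misalignment is real and small. On the protocol's literal wording, the first-year window passes the end of routine non-serious capture by the consent-to-dose gap. The Total-group non-serious AE rate is then understated relative to a matched window by 0% with same-day consent, and by about 1.9%, 3.8% or 7.7% for full-year subjects with assumed gaps of 7, 14 or 28 days. The proportional effect can be larger in the 300 mg group for subjects who switch late in year 1.

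A general statement that first-year rates are understated would go too far. The mixed rates are only partly affected. In the 300 mg group, the first-year formula also gives zero or negative days when 300 mg starts 365 days or more after first dose (for example 364 − 392 + 1 = −27). That is a separate defect, and it pushes that group's rate upward.

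The missing last-dose+85 limit is a minor inconsistency of at most about 7 days per subject followed on schedule. The end-of-study date for lost subjects needs a definition.

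**What to change.** - **End each first-year window at the actual end of non-serious capture.** Add consent date+364 to the minimum in every first-year formula, and count only events inside that window. If data were in fact collected for 365 days from first dose, say so in Protocol 6.1.1 and 6.4.1 and in SAP 3.8.4, and keep first dose+364.
- **Use the same last-dose+85 limit in both sets of formulas.** For the Total group, the first-year window would then end at the earliest of end of study, last dose+85, first dose+364 and consent+364.
- **Define the end-of-study date for lost subjects as last contact.** The +85 limit alone is not enough, because a subject lost straight after a dose would still contribute 85 days without data.

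The cost is a few terms in the SAP formulas, using dates the study already needs. Person-time falls slightly. A few SAEs captured late in the year drop out of the first-year treatment-emergent rate, but they remain in the SAE rate.

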4.5.3 Treatment Regimen

Subjects will receive MEDI-546 300 mg administered as an IV infusion Q4W starting at Day 1 (Week 0) or the visit following approval of this amendment (for those subjects who

have already been dosed in this study) for up to 3 years or until the sponsor discontinues development of MEDI-546 for SLE, whichever comes first.

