5.2.4 Tuberculosis Testing

A QFT-GIT will be performed at Day 1 for all subjects who tested negative or indeterminate at Day 337 in Study CD-IA-MEDI-546-1013. If a subject missed being tested at Day 1, a QFT-GIT should be performed at the next scheduled visit and then per protocol. An annual TB screen is not required for subjects who have tested positive and have been treated for latent TB in Study CD-IA-MEDI-546-1013.

Upon approval of Study CD-IA-MEDI-546-1145 Protocol Amendment 4, any subject whose last QFT-GIT result was negative or indeterminate (whether in this study or in Study CD-IA-MEDI-546-1013) and has not had a QFT-GIT performed in the previous year (from local approval date) should have it performed at the next scheduled visit and then per protocol.

All subjects must be evaluated by the physician for clinical signs/symptoms of active TB prior to each scheduled infusion visit using a TB surveillance form. If the evaluation raises suspicion that a subject may have a new or reactivated TB, an immediate and thorough investigation should be undertaken, including where possible, consultation with experts specializing in TB. Please note that TB in immunocompromised subjects may present as disseminated disease or with extrapulmonary features and should be referred for appropriate treatment.

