2.2 Study Design

This is an open-label, multinational, multicenter study to evaluate the long-term safety and tolerability of anifrolumab in adult subjects with chronic, moderately-to-severely active SLE who were previously treated with investigational product (anifrolumab 300 mg, 1000 mg, or placebo) and completed study CD-IA-MEDI-546-1013 (CD1013) through treatment (48 weeks dosing) and follow-up (85 days) periods. The start of this OLE study (first dose) should occur within 28 days of the last visit of study CD1013 or at the discretion of the medical monitor if the start of this OLE study occurs outside the 28-day window.

Approximately 240 subjects will be enrolled to receive IV anifrolumab as a 1000 mg fixed dose administered over at least 30 minutes every 4 weeks starting at Day 1 (Week 0) for up to 3 years or until the sponsor discontinues development of anifrolumab for SLE, whichever

[REDACTED]

comes first. The dose was changed to 300 mg on 12Feb2015 (protocol amendment 4) as the efficacy and safety data from study CD1013 indicated that the 300 mg dose had a more favorable benefit:risk profile than the 1000 mg dose. All subjects will be followed for 85 days after receiving their last dose of anifrolumab.

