3.2.2 Treatment Groups for Analysis

Treatment group is Anifrolumab Total for all analyses except the exposure adjusted adverse event which will be summarized by Anifrolumab 300 mg, Anifrolumab 1000mg, and Anifrolumab Total.

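### SAP 3.8.4: the first-year 300 mg exposure formula has no floor at zero, so subjects who reach 300 mg on OLE Day 367 or later contribute negative person-time and inflate five 300 mg event rates

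*SAP*

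**What the plan says.** SAP 3.2.2 uses a single pooled group everywhere except for the "exposure adjusted adverse event which will be summarized by Anifrolumab 300 mg, Anifrolumab 1000mg, and Anifrolumab Total". SAP 3.8.4 divides the number of subjects with an event by summed exposure time, scaled to 100 patient-years.

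There are two exposure windows. Discontinuation events, deaths, SAEs and AESIs use a window that is not cut at one year: "Anifrolumab 300 mg group: duration of exposure (days) = minimum(end of study date in CD1145, last dosing date in CD1145+85 days"). The other five categories (treatment-emergent, non-serious, acute and product-related events, and events by worst severity) use a first-year window, because non-serious events are collected only in year one. For these five, the 300 mg rule starts "Anifrolumab 300 mg group: minimum(end of study date in CD1145, first dosing date in CD1145+364") and then subtracts the first 300 mg dose date and adds 1. The paired 1000 mg rule for subjects who had both doses is capped: "minimum(first dosing date in CD1145+364, first dosing date of 300 mg-1"), minus the first dose date, plus 1. On the numerator, the section adds "The events occurred during the exposure period will be included in the summary".

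SAP 2.2 dates the dose change: "The dose was changed to 300 mg on 12Feb2015 (protocol amendment 4"). Protocol 4.5.3 moves subjects already on treatment to 300 mg at Day 1 "or the visit following approval of this amendment". Protocol 5.2.4 times another Amendment 4 requirement by site approval ("has not had a QFT-GIT performed in the previous year (from local approval date")), which suggests that switch dates vary between sites. Protocol 3.2 gives 156 weeks of treatment.

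**The concern.** A subject can be well past the first year in the extension when first given 300 mg. The first-year window then closes before 300 mg exposure begins, and the formula returns a negative number of days. Nothing in SAP 3.8.4 sets that to zero or removes the subject. The rule on which events count does not help, because it restricts the numerator only.

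The cap in the 1000 mg rule changes the result only for a switch on Day 367 or later. The SAP therefore provides for these subjects in the 1000 mg column and not in the 300 mg column.

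The exposure-adjusted table is the only place where adverse events are split by dose, and treatment-emergent events are central to the primary endpoint (Protocol 7.3.1). The error raises the 300 mg rates and leaves the 1000 mg rates alone, so it would distort the comparison between doses against 300 mg.

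**Working it through.** The SAP states no exposure total or rate to reproduce, so the check evaluates its formulas directly.

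**Notation.** F = first dose date in the extension (OLE Day 1); S = first 300 mg dose date, on OLE Day d, so S = F + d − 1; E = end-of-study date.

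**Formulas (SAP 3.8.4, first-year window, subjects given both doses).**
- Total: min(E, F+364) − F + 1
- 1000 mg: min(F+364, S−1) − F + 1
- 300 mg: min(E, F+364) − S + 1

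**Per subject.** A subject dosed on Day 366 or later is necessarily still on study at F+364, so the minimum is F+364 and

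300 mg days = (F+364) − (F+d−1) + 1 = 366 − d.

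For d ≤ 365 the result is at least 1 for any E on or after S. For a subject still on study at Day 365:

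| d | 1000 mg | 300 mg | Sum | Total |
|---|---|---|---|---|
| 169 | 168 | 197 | 365 | 365 |
| 365 | 364 | 1 | 365 | 365 |
| 366 | 365 | 0 | 365 | 365 |
| 367 | 365 | −1 | 364 | 365 |
| 449 | 365 | −83 | 282 | 365 |
| 533 | 365 | −167 | 198 | 365 |

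The two dose columns add to Total up to Day 366 and fail from Day 367, where the sum is 731 − d.

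**Calendar.** A switch on 12 Feb 2015 itself gives negative days if F is 11 Feb 2014 or earlier, and a later switch moves that cutoff later. Worked case with assumed dates: F = 1 Jul 2013 and first 300 mg dose at the first 28-day visit on or after 1 Apr 2015. That visit is 6 Apr 2015, 23 × 28 = 644 days after F, so d = 645 and the exposure is 366 − 645 = −279 days.

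**Effect on a rate.** The numerator is the same with and without a floor, so inflation = floored days / days as written. With 20% late switchers at mean Day 450 (−84 days each) and 80% at mean Day 250 (116 days each), both assumed:
- floored: 0.8 × 116 = 92.8 days per subject
- as written: 92.8 − 0.2 × 84 = 76.0
- inflation: 92.8 / 76.0 = 1.22

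**Illustration by calendar (all dates assumed).** Uniform daily entry from the date shown to 31 Mar 2015, no dropout, and the first 300 mg dose at the first 28-day visit on or after the switch date. Cells show mean 300 mg days per subject as written / floored, then the inflation.

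| Entry from | Switch 1 Apr 2015 | Switch 1 Jun 2015 |
|---|---|---|
| Apr 2013 | −14.0 / 84.3, negative | −75.0 / 57.6, negative |
| Jul 2013 | 31.4 / 96.3, 3.1-fold | −29.4 / 65.8, negative |
| Oct 2013 | 77.3 / 112.5, 1.5-fold | 16.5 / 76.8, 4.7-fold |
| Jan 2014 | 123.3 / 135.2, 1.1-fold | 62.4 / 92.4, 1.5-fold |
| Apr 2014 | 168.5 / 168.5, none | 107.5 / 115.1, 1.07-fold |

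In the first four rows late switchers make up 20–59% of subjects.

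**Sensitivities on those eight scenarios.**
- 20% per year dropout before the switch: 1.1- to 7.5-fold in six, negative in two.
- 20% of the group starting directly on 300 mg (365 days each): 1.06- to 9.2-fold, none negative.
- Both together: 1.05- to 3.7-fold, none negative.

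**The case against.** The best counter-argument is that the intent can be recovered. A period that ends before it begins is empty, and the 1000 mg cap already gives a late switcher's whole first year to 1000 mg. A careful programmer would set the 300 mg days to zero, and the separate statistical programming plan (SAP 1), which is not available, may say so. On this view nothing is wrong until code sums negative durations.

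The size is also not established. The documents give neither extension entry dates nor switch dates. Of the ten calendar scenarios, three are negative and two show 7% inflation or less. They assume that nobody starts directly on 300 mg, although the protocol allows for it. With 10% direct starters only one of the first eight scenarios is negative, and with 20% none is. A table that displays patient-years could also expose the problem. The study is single-arm and descriptive, so no test depends on it.

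The uncertainty about size stands, and so does the point that the programming plan may contain a floor. Neither removes the defect. The SAP writes this formula out in full rather than deferring it, and as written it gives the wrong denominator. A negative total would be noticed, but a rate inflated by 10–50% carries no warning of its own.

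**Conclusion.** The concern holds, and it should be fixed. The formula is wrong as written from OLE Day 367, by exactly d − 366 days per late switcher. That result needs no assumption beyond the SAP's own definitions. The bias is upward for as long as the summed days stay positive; after that the rate is undefined or negative.

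The group effect depends on how many subjects switched late and how late, and on the formula being programmed literally. Under the assumed dates it runs from nothing to an unusable rate, so those figures are illustration and not an estimate.

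The scope is limited to the 300 mg column of five categories. The 1000 mg and Total columns are sound, and so are the 300 mg rates for SAEs, AESIs, deaths and discontinuation events.

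**What to change.** In SAP 3.8.4, define first-year 300 mg exposure as max(0, min(E, F+364) − S + 1), with E, F and S the end-of-study, first extension dose and first 300 mg dose dates. This alone corrects the rates.

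For the five first-year categories, also limit the 300 mg numerator, person-time and displayed N to subjects with S on or before F+364, and footnote the smaller N. This makes the display match the denominator and does not change the rate.

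Add a program check that 1000 mg days plus 300 mg days equal Total days for every subject. With the floor, this held for every switch day tested from 1 to 729.

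The cost is one line in the SAP, one condition in the program and one footnote. The five 300 mg rows will show a smaller N than the rest of the column.
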